**Stop Dates:**

1. If the year is unknown, then the date will not be imputed and will be assigned a missing value.
2. If the month is unknown, then 'December' will be assigned.
3. If the day is unknown, then the last day of the month will be assigned.

### **8.3 Protocol Deviations**

Protocol deviations will be classified as major/minor by the MPBC protocol deviations review committee. The committee will determine the impact of the deviation on the study subjects' safety and rights, study compliance, data quality, and the proposed analyses. A subject level listing will report the description of the deviation and the impact.

A table of protocol deviations will summarize them by major/minor into the following categories:

- Informed Consent
- Inclusion/Exclusion
- Study Treatment
- Prohibited Concomitant Medication
- Trial Procedures
- Safety Reporting
- Discontinuation
- Miscellaneous

### **8.4 Baseline Values**

Baseline values are from Baseline Visits for all measures, except C-SSRS, AUDIT, DUDIT, resting blood pressure (BP), Body Mass Index (BMI). For C-SSRS, the initial screening visit will be conducted with the 'Lifetime' version of the measure. The Independent Rater Screening assessment of 'Since Last Visit' suicidal ideation and behavior will be used as 'Baseline.' For the AUDIT and DUDIT measures and resting BP, BMI, results collected at Screening will be used as the Baseline value.

### **8.5 Participant Disposition and Dosing Summary**

The Safety Set will be included in the summary of participant disposition and accountability summarized. The number and percent of participants who completed or discontinued the study will be displayed with reasons for early termination, where the percent is with respect to the total number of participants. The timepoint of doses and total MDMA (mg) administered will be summarized for the Safety Set.

## 8.6 Demographics and Baseline Characteristics

Participant demographic data and Baseline characteristics will be summarized descriptively.

## 8.7 Efficacy Analyses

For all primary, secondary, and exploratory endpoints descriptive statistics (n, mean, standard deviation, median, range, or counts and percentages where appropriate) will be provided. Longitudinal PCL-5 and SDS item scores will be plotted across visits to characterize the onset of treatment effect.

### 8.7.1 Primary Effectiveness Analysis

The primary analysis of the effectiveness of MDMA-assisted psychotherapy will be made using a Mixed Model Repeated Measure (MMRM) model to assess changes in PCL-5 scores throughout the study period from Baseline (Visit 3) through Visit 16. Baseline covariates (baseline PVL-5, age, gender, ethnicity, index trauma, complexity and severity of trauma, diagnosis of comorbid depression, diagnosis of comorbid Axis 2 diagnosis, adverse childhood experiences collected in the parent study) may be assessed for inclusion in the final model with an alpha level set at 0.05.

### 8.7.2 Secondary Effectiveness Analysis

The SDS will be analyzed in a similar manner to the primary analysis of the PCL-5.

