6.2 Secondary Measure

6.2.1 SDS (Sheehan Disability Scale)

The SDS is a 5-item measure of functional impairment [72]. The items indicate degree of impairment in the domains of work/school, social life, and home life, with response options based on a 10-point scale (0=not at all to 10=extremely), and five verbal tags (not at all, mildly, moderately, markedly, extremely). The SDS has high internal consistency and accurately identified 80% of a sample of primary care patients with mental disorders [73]. The Customized version of the SDS for PTSD for MAPS was developed utilizing the standard SDS. The first three items indicate degree of impairment in the domains of work/school, social life, and home life, with response options based on a 10-point scale (0=not at all to 10=extremely), and five verbal tags (not at all, mildly, moderately, markedly, extremely). The remaining two items assess Days Lost and Days Unproductive during the reporting period. The SDS for PTSD for MAPS maintains the same scale conventions as the standard SDS. To limit missing data, the summary measure used to analyze the treatment effect on SDS is the mean of the 3 item responses at each visit. Any participant who did not work during the reporting period due to reasons related to PTSD is scored as maximal work-related impairment on item 1. Any participant who did not work during the reporting period due to reasons not related to PTSD reports on the reason for not working and Item 1 is skipped. The SDS for PTSD for MAPS has been approved by the author ([name]) for use in MAPS Research and is referred to throughout the protocol as SDS. The SDS for PTSD for the MAPS takes approximately 5 minutes to complete.

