10.1.7 Participant Discontinuation or Withdrawal from Study

Reasons why a participant may discontinue or be withdrawn from the study may include but are not limited to:

- Development of toxicity which in the investigator's judgment precludes further therapy
- Participants request
- Participant non-compliance
- Intercurrent illness
- At the discretion of the investigator
- Pregnancy
- Study termination by the sponsor
- Protocol violation

When a participant is withdrawn, the investigator will notify the sponsor and clearly document in the medical record and appropriate case report form the reason for withdrawal from study. When possible, the investigator will perform the procedures indicated for the final visits within 30 days after the last medication dose.

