13.2.1.2 Secondary Outcome

The SDS will be analyzed in a similar manner to the primary analysis of the PCL-5. Details of analysis are described in the Statistical Analysis Plan.

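### Does the SDS analysis need fuller specification, given that the scale is collected only at Visits 3 and 16?

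*SAP*

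**What the plan says.** Protocol 13.2.1.2 defers to the SAP for the SDS: "Details of analysis are described in the Statistical Analysis Plan". SAP 8.7.2 replies with a single sentence, "The SDS will be analyzed in a similar manner to the primary analysis of the PCL-5", which the protocol already contains.

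The analysis being borrowed, in SAP 8.7.1, is an MMRM on the PCL-5 from Visit 3 to Visit 16. Its candidate covariates begin "Baseline covariates (baseline PVL-5, age, gender, ethnicity, index trauma" and "may be assessed for inclusion in the final model with an alpha level set at 0.05". The first item is evidently baseline PCL-5. Protocol 13.2.1.1 lists no baseline score among its candidates.

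The measures tables in both documents schedule the SDS at Visits 3 and 16 only. SAP 8.7 nevertheless plans that "Longitudinal PCL-5 and SDS item scores will be plotted across visits to characterize the onset of treatment effect".

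Scoring is in Protocol 6.2.1: "the summary measure used to analyze the treatment effect on SDS is the mean of the 3 item responses at each visit". A participant not working because of PTSD receives the maximum on item 1. For one not working "due to reasons not related to PTSD reports on the reason for not working and Item 1 is skipped". SAP 3.2 defines the endpoint as the mean change in SDS item scores between the two visits.

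**The concern.** The protocol sends the reader to the SAP for details, and the SAP sends the reader back to a model built for a different visit schedule. With one post-baseline SDS value there is no repeated post-baseline structure to model. What remains is either a paired comparison, with Visit 3 and Visit 16 both as responses, or an ANCOVA, with change as the response and Visit 3 as covariate. By analogy with the PCL-5, a 0.05 screen could decide between them. In a one-arm study the mean change and its interval are the result, so an unstated choice that affects interval width looks like a real gap.

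Two smaller points add to it. If item 1 is skipped at one visit and scored at the other, the two means rest on different items. And a line joining two points says nothing about when improvement began.

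**Working it through.** The documents give no SDS standard deviation, correlation, effect size or power figure, so there is no stated result to reproduce. SDs and correlations below are assumptions.

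**1. Where the SDS is collected.** Protocol measures table, minutes at Visits 6, 10 and 14: C-SSRS 10 + LEC-5 5 + PCL-5 8 = 23, as printed. Adding the SDS (5) would give 28. The printed totals at Visit 3 (55) and Visit 16 (61) do include it. There is one post-baseline value.

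**2. Timing (visit windows, Protocol Table 1).**
- PCL-5 at Visit 6: 1 + 10 = 11 to 14 + 18 = 32 days after Visit 3.
- SDS at Visit 16, all three sessions completed: 1 + 21 + 21 + 24 = 67 to 14 + 56 + 56 + 32 = 158 days after Visit 3.

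Protocol 7.4 has treatment withdrawers assessed at once, so theirs can come earlier. It is still a single value.

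**3. Paired form against covariate form, complete data.** With Visit 3 as the only covariate, evaluated at its sample mean, both forms return the observed mean change. The standard errors differ:

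SE(ANCOVA) / SE(paired) = √(1 − R²), where R² is the squared correlation of change with Visit 3.

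For correlation ρ and SD ratio k (Visit 16 over Visit 3): R² = (kρ − 1)² / (k² + 1 − 2kρ). At k = 1 this is (1 − ρ)/2.

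| k | ρ | R² | SE ratio | Coverage of population mean change by a nominal 95% ANCOVA interval |
|---|---|---|---|---|
| 1.0 | 0.3 | 0.35 | 0.806 | 88.6% |
| 1.0 | 0.5 | 0.25 | 0.866 | 91.0% |
| 1.0 | 0.7 | 0.15 | 0.922 | 92.9% |
| 1.3 | 0.3 | 0.195 | 0.90 | about 92% |
| 1.3 | 0.5 | 0.088 | 0.96 | about 94% |
| 1.3 | 0.7 | 0.009 | 0.995 | about 95% |

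Coverage is 2Φ(1.96 × ratio) − 1. Simulation at k = 1 (n = 100, 20,000 runs per setting) gave 88.3%, 91.3% and 92.8% for ANCOVA, and 94.7%, 95.0% and 94.9% for the paired form. The ANCOVA shortfall arises because its interval is conditional on the observed Visit 3 scores; it is a correct interval for that narrower target.

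**4. The 0.05 screen, n = 100.** F = R²/(1 − R²) × 98. At R² = 0.15, F = 17.3 and Visit 3 is kept. At R² = 0.009, F ≈ 0.9 and it is usually dropped, but there the two intervals are almost identical.

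**5. Missing Visit 16 values.** Assume SD 2.3, ρ = 0.5, N = 100 and 7.5% missing (the Phase 2 dropout rate in Protocol 1.2.4, used for illustration). SEs are 0.240 for change in completers, 0.237 for the two-visit model using all Visit 3 data, and 0.208 with Visit 3 as covariate. The first two differ by about 1%; 0.208/0.240 = 0.87 matches step 3.

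**6. Item 1 skipped at one visit.** Let items 2 and 3 average m and stay unchanged. Item 1 is 10 at Visit 3 and skipped at Visit 16, and the score is the mean of answered items. Change = m − (10 + 2m)/3 = (m − 10)/3.

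| m | Change in that participant | Shift in mean of 100 | Participants needed for 0.5 points |
|---|---|---|---|
| 4 | −2.00 | −0.020 | 25 |
| 6 | −1.33 | −0.0133 | 38 |
| 8 | −0.67 | −0.0067 | 75 |

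The reverse move has the opposite sign, so only the net number counts.

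**The case for a change.** The case for amending the SAP is that this is the key secondary endpoint, neither document specifies its model, and the two documents imply different candidate covariates. The remedy would be a few sentences with no new data. An analyst who chose the form after seeing the data could pick the narrower interval, by up to 19% in the settings above. A Visit 16 SD below the Visit 3 SD would widen that gap. Missing values also matter: dropouts who agree to a last assessment are asked only for a PCL-5 (Protocol 4.4.4), and the request in Protocol 10.1.7 to "perform the procedures indicated for the final visits within 30 days after the last medication dose" applies only when possible. With Visit 16 missing, the forms no longer use exactly the same participants.

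The factual part stands: the form is unstated, the denominator after a skip is unstated, and equality of the estimates needs complete data. The consequence is weaker. SAP 8.7 already requires n, mean and SD for every secondary endpoint, and SAP 3.2 makes that endpoint the change. If change is summarised as defined, the paired interval follows directly and a reader can set it beside any model result. Participants who stop treatment but remain in the study stay in secondary outcome follow-up (Protocol 4.4.4). SAP 8.0 fixes the SDS test as two-sided at 0.05. On scoring, Protocol 6.2.1 states when item 1 is skipped, and its stated aim of limiting missing data points to averaging the answered items.

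**Conclusion.** No change to the plan follows. The SDS analysis is thinly described, but the visit schedule leaves only two sensible forms. Both are valid and, with complete Visit 16 data, give the same estimate. The interval differs by roughly 0% to 19% for correlations of 0.3 to 0.7 and SD ratios of 1.0 to 1.3. Those inputs are assumed, and the largest differences need equal SDs and a low correlation. The paired result can be recovered from the planned descriptive statistics.

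The skip rule is written down apart from its denominator, which has one natural reading and little leverage on the group mean. The number of participants whose item 1 status changes between visits is unknown, but it would have to be large and one-directional to matter. The onset wording pairs the SDS with the PCL-5 in a sentence about descriptive plots; the PCL-5 supplies the intermediate visits, and a two-point SDS plot misleads no one.

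With one arm, no powered hypothesis and a sample size not set on statistical grounds, these are gaps in detail that do not bear on the study's conclusion.

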### 8.7.3 Exploratory Analyses

Post-hoc exploratory analyses not identified in this SAP may be performed to further examine the study data. In particular, MMRM models, linear regression, and/or ANCOVA models may be utilized to analyze the effect of MDMA in conjunction with psychotherapy on the following exploratory endpoints:

- Presence of secondary traumatic stressors identified on the Life Events Checklist (LEC-5) on the PCL-5 total severity analysis
- Depression (BDI-II)
- Chronic pain (CPGS)
- Quality of life (EQ-5D-5L)
- Nicotine use (SRNU)
- Eating habits (EAT-26)
- Workplace productivity (HPQSF)
- Alcohol use (AUDIT)
- Drug use (DUDIT)

These analyses will be clearly identified as exploratory in the final clinical study report.

## 8.8 Safety Analyses

Safety analyses will confirm safety data with summary tables listing exposure to IMP, unsolicited AEs, TEAEs, concomitant medications, suicidal ideation and behavior, and vital signs overall and by group. If a participant has more than one AE mapped to the same PT, that AE will be reported once using the highest severity. AEs that occur on Day 0 (Experimental Session), Day 1, Day 2

after IMP administration will be presented separately. Compare relative incidence of AEs during Experimental Sessions such as clinical signs and symptoms, such as chest pain, shortness of breath, or neurological symptoms or any other signs or symptoms that may be indicative of a medical complication of the IMP.

### **8.8.1 Analysis of Exposure**

The total mg exposure of participants will be summarized. Data will be tabulated for the Safety Set.

### **8.8.2 Analysis of Adverse Events**

The primary measure of safety will be the reporting of unsolicited AEs. All AEs collected from Enrollment to Termination will be categorized as follows:

- Pretreatment AEs are defined as AEs that occur during the Preparatory Period prior to the first dose in the first Experimental Session
- Treatment Emergent AEs are defined as AEs that occur during the Treatment Period from the first Experimental Session to the last Integrative Session
- AEs that occur on and two days after MDMA administration
- AESIs are defined as AEs specified in the protocol related to cardiac function and abuse liability
- Follow-up Period AEs are defined as AEs that occur during the Follow-up Period after the last Integrative Session through Termination
- AEs leading to discontinuation of IP
- AEs resulting in death or hospitalization.
- SAEs
- AEs continuing at Termination.

Verbatim terms on case report forms will be mapped to preferred terms (PT) and system organ class (SOC) using the Medical Dictionary for Regulatory Activities (MedDRA) Version 24.0. Frequency and incidence of AEs will be displayed by PT, sorted by SOC, severity, and seriousness. AEs will be analyzed and presented as follows:

- If a participant has more than one AE mapped to the same PT, that AE will be reported once using the highest severity
- Relationship will be determined by the Clinical Investigator
- AEs that occur on day of Experimental Sessions and two days after IP administration will be presented separately.

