2.3 Safety Objectives

The overall safety objective is to assess severity, incidence and frequency of Adverse Events (AEs), Treatment Emergent AEs (TEAEs), AEs of Special Interest (AESIs), and Serious Adverse Events (SAEs), concomitant medication use, suicidal ideation and behavior, and vital signs to support the package insert for MDMA-assisted therapy. The following safety objectives will evaluate the safety of MDMA-assisted therapy:

- 1. Assess incidence of AEs during Experimental Sessions that may be indicative of a medical complication of the Investigational Medicinal Product (IMP) such as clinical signs and symptoms of chest pain, shortness of breath, or neurological symptoms or any other signs or symptoms that prompt additional vital sign measurements
- 2. Assess incidence of AEs by severity
- 3. Assess incidence of TEAEs by severity
- 4. Assess incidence of TEAEs by severity reported during an Experimental Session, 1 day, and 2 days after IMP administration
- 5. Assess incidence of AESIs, defined as AEs specified in the protocol related to cardiac function, suicidality, and abuse liability
- 6. Assess incidence of AEs by severity categorized as leading to discontinuation of IMP, resulting in death or hospitalization, and continuing at Study Termination
- 7. Assess incidence of SAEs
- 8. Assess incidence of concomitant medications taken during an Experimental Session, 1 day, and 2 days after IMP administration
- 9. Assess incidence of psychiatric concomitant medications taken during the Treatment Period
- 10. Assess incidence of positive or serious suicidal ideation and positive suicidal behavior assessed with the Columbia Suicide Severity Rating Scale (C-SSRS)
- 11. Assess changes in blood pressure (BP), heart rate, and body temperature from pre-IMP administration to end of each Experimental Session

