7.3.2 Telephone Contact After Experimental Sessions

The goal of the telephone contact is to assess health changes, ensure participant safety, and offer support. The therapy pair will follow-up with the participant by telephone every other day for 14 days after each Experimental Session. If an Integrative Session falls on the date of a planned phone call, the phone call does not need to be performed. Each call will last on average 5 to 20 minutes but could be longer to address participant concerns and to adequately assess wellbeing. Additional telephone contact can be initiated at the request of the therapy pair or participant.

At each telephone contact, the therapy pair will:

- Inquire about any possible changes in health, assess the participant's mental health and the status of any previously recorded AEs, and record AEs as described in Section 10.0 Safety.
- Administer the Since Last Visit C-SSRS.
- Inquire about concomitant medication use and adherence.
- Offer support in accordance with the Treatment Manual.

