7.3.3 Integrative Sessions

After each Experimental Session, three Integrative Sessions will take place. Each session will consist of 90 minutes of therapy. Integrative Sessions should not be less than 48 hours apart. The therapy pair may record the sessions. Integrative Sessions 1.2, 1.3, 2.2, 2.3, 3.2, and 3.3 may be performed via telemedicine.

MAPPUSX Protocol

Amendment 3 Version 1: 15 March 2023

Treatment 1

- Integrative Session 1.1 (Visit 5): morning after Experimental Session 1 (Visit 4).
- Integrative Session 1.2 (Visit 6): 10 to 18 days after Experimental Session 1 (Visit 4). The participant will complete the PCL-5 and LEC-5.
- Integrative Session 1.3 (Visit 7): at least 2 days after Integrative Session 1.2 (Visit 6) and 1 to 14 days in advance of Experimental Session 2 (Visit 8). This visit serves two purposes: to continue integration and to prepare for the next Experimental Session.

Treatment 2

- Integrative Session 2.1 (Visit 9): morning after Experimental Session 2 (Visit 8).
- Integrative Session 2.2 (Visit 10): 10 to 18 days after Experimental Session 2 (Visit 8). The participant will complete the PCL-5 and LEC-5.
- Integrative Session 2.3 (Visit 11): at least 2 days after Integrative Session 2.2 (Visit 10) and 1 to 14 days in advance of Experimental Session 3 (Visit 12). This visit serves two purposes: to continue integration and to prepare for the next Experimental Session.

Treatment 3

- Integrative Session 3.1 (Visit 13): morning after Experimental Session 3 (Visit 12).
- Integrative Session 3.2 (Visit 14): 10 to 18 days after Experimental Session 3 (Visit 12). The participant will complete the PCL-5 and LEC-5.
- Integrative Session 3.3 (Visit 15): at least 2 days after Integrative Session 3.2 (Visit 14).

During Integrative Sessions, the therapy pair will:

- Inquire about any possible changes in health. Assess the participant's mental health and the status of any previously recorded AEs. Record AEs as described in Section 10.0 Safety.
- Inquire about concomitant medication use and adherence.
- Administer Since Last Visit C-SSRS to determine suicidal risk.

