7.4 Study Termination

Study Termination (Visit 16) will take place 24 to 32 days after the Experimental Session 3 (Visit 12) and after the last Integrative Session 3.3 (Visit 15). Participants who have withdrawn from treatment but have continued for follow-up will also complete this assessment immediately upon withdrawal.

The site team will:

- Inquire about any possible changes in health. Assess the participant's mental health and the status of any previously recorded AEs. Record AEs as described in Section 10.0 Safety.
- Inquire about concomitant medication use and adherence.
- Administer Since Last Visit C-SSRS.
- Measure weight (used to calculate BMI).
- Measure blood pressure.
- Perform urine pregnancy test for participants who are able to become pregnant.
- Provide and discuss a study Exit Plan/Plan for Moving Forward.
- Ask them to enroll into the LTFU extension study with a visit at least 6 months after the last Experimental Session. Review contact information and Informed Consent procedures for LTFU.
- Actively support participant in completion of Study Termination self-reported measures. Completion of the measures does not need to be recorded.
 - o LEC-5
 - o PCL-5, under the direction of the therapy pair, who will remind them of the index trauma listed in the parent study to which PTSD symptoms should be anchored
 - o SDS
 - o BDI-II
 - o CPGS
 - o EQ-5D-5L
 - AUDIT
 - o DUDIT
 - SRNUEAT-26
 - HPOSF

After all Study Termination measures and assessments are completed, the participant is considered terminated from the study. The participant can resume normal everyday life.

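### SAP 8.8.2 closes the treatment-emergent window at a therapy visit rather than at a set time from dosing, so scheduling decides which late AEs count as TEAEs

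*SAP*

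**What the plan says.** The definition in SAP 8.8.2 is: "Treatment Emergent AEs are defined as AEs that occur during the Treatment Period from the first Experimental Session to the last Integrative Session". The next period is set apart from it: "Follow-up Period AEs are defined as AEs that occur during the Follow-up Period after the last Integrative Session through Termination". An event after the last Integrative Session is therefore a Follow-up event and not a TEAE. The protocol uses the term TEAE in its objectives (2.3) but does not define it, so the SAP wording governs.

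The protocol (7.3.3) sets the visits that fix the end of the window after the third dose. The first of these has a fixed time: "Integrative Session 3.1 (Visit 13): morning after Experimental Session 3 (Visit 12". The second is given a range of days: "Integrative Session 3.2 (Visit 14): 10 to 18 days after Experimental Session 3 (Visit 12". The third has only a minimum gap: "Integrative Session 3.3 (Visit 15): at least 2 days after Integrative Session 3.2 (Visit 14". No latest day is given for Visit 15, except that Visit 16 comes after it (7.4): "Study Termination (Visit 16) will take place 24 to 32 days after the Experimental Session 3 (Visit 12". AEs are collected until the termination visit, give or take 2 days (10.1). AEs are also recorded in the calls after each dose (7.3.2): "The therapy pair will follow-up with the participant by telephone every other day for 14 days after each Experimental Session".

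Safety objective 4 (Protocol 2.3, repeated in SAP 3.3) reads: "Assess incidence of TEAEs by severity reported during an Experimental Session, 1 day, and 2 days after IMP administration".

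**The concern.** A treatment-emergent window is normally anchored to dosing. Here it ends at a therapy visit whose timing varies between participants. Two people with the same dosing and the same event on the same day after dose 3 can be classified differently only because of when Visit 15 was booked. Relative to a window that runs to the end of AE collection, the rule can only lower the TEAE count.

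TEAE incidence by severity is safety objective 3 of a study described as a safety extension, and the safety results are intended for product labelling. Protocol Table 9 recognises that psychological distress may arise after the drug effect has worn off, while the experience is being integrated. Late events are the ones that this cut-off can relabel.

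There is a second problem for participants who stop before Visit 15. Neither document says what the last Integrative Session is for them, so the rule cannot be programmed for these participants without a further decision.

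**Working it through.** The plan gives no figure to reproduce. The check is a day count on the protocol's visit windows, in days after the last dose.

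**Inputs.** Visit 13: day 1. Visit 14: day 10 to 18. Visit 15: at least 2 days after Visit 14 (all Protocol 7.3.3). Visit 16: day 24 to 32, after Visit 15 (7.4). AE collection: to Visit 16, ±2 days (10.1). Calls: 14 days (7.3.2).

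**Completers.** Days outside the TEAE window = Visit 16 day − Visit 15 day.

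- Earliest Visit 15: 10 + 2 = day 12.
- Visit 15 on day 12, Visit 16 on day 24: 24 − 12 = 12 days; 12/24 = 50%.
- Visit 15 on day 12, Visit 16 on day 32: 32 − 12 = 20 days; 20/32 = 62.5%.
- The same, using the 2 extra collection days: 34 − 12 = 22 days; 22/34 = 65%.
- Visit 15 just before Visit 16: about 0 days.
- Mid-window: Visit 14 on day (10 + 18)/2 = 14 and Visit 16 on day (24 + 32)/2 = 28. With Visit 15 at its earliest, day 16, the gap is 28 − 16 = 12 days (43%). With Visit 15 on an assumed day 21, halfway between the two, it is 28 − 21 = 7 days (25%).
- All permitted whole-day combinations with equal weight: mean 6.5 days, median 6. This describes the windows and is not a forecast, because actual scheduling is unknown.

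If Visit 15 is on day 12, the window closes 14 − 12 = 2 days before the phone follow-up ends. An AE that starts on day 15 is a Follow-up event for a participant with Visit 15 on day 12, and a TEAE for one with Visit 15 on day 20.

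**Participants who never reach Visit 15.** Two readings are open.

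1. *Last attended.* If the only session after a dose was the next-morning one, the window closes on day 1. If AEs are then collected to day 10, 18 or 30 (illustrative), the days outside are 9/10 = 90%, 17/18 = 94% or 29/30 = 97%. A Day 2 event is not a TEAE, contrary to the wording of objective 4. Someone who leaves after dose 2 or 3 but before the next-morning session last attended one 1 to 14 days before that dose (Protocol Table 1), so every AE of that dose falls outside.
2. *Planned Visit 15.* Protocol Table 1 ends the Treatment Period at Visit 15. A participant without that visit has no defined end of window.

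**Who carries the excluded time.** Assume N = 100, the 7.5% dropout rate (8 of 107) of the earlier Phase 2 studies (Protocol 1.2.4), reading 1, 9 to 29 excluded days per early leaver and 7 to 20 per completer. That gives 7.48 leavers and 92.52 completers.

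- Lowest leaver share: 7.48 × 9 = 67 person-days against 92.52 × 20 = 1,850; 67/1,917 = 3.5%.
- Highest leaver share: 7.48 × 29 = 217 against 92.52 × 7 = 648; 217/865 = 25%.

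Most of the excluded time sits with completers.

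**With the window run to Study Termination or last contact,** no collected post-dose day is excluded for anyone.

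**The case against.** The best defence has four parts.

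- **Nothing is hidden.** SAP 8.8.2 categorises all AEs from Enrollment to Termination. A late event appears as a Follow-up AE and, where it applies, among SAEs, AEs leading to discontinuation, deaths or hospitalisations, and AEs continuing at Termination. AEs on the dosing day and the two days after are presented separately whatever their TEAE flag. This stands. A reader might infer that delayed events vanish from the safety report, and the documents do not support that. Only the TEAE label is at issue, and the conflict over Day 2 is one of wording under a single reading.
- **The cut-off is pharmacologically generous.** The half-life is 7 to 9 hours (Protocol 1.2.2), so five half-lives are 35 to 45 hours, while every completer who keeps to the visit windows has at least 12 days. The anxiety and low mood mentioned in Appendix A at 1 to 3 days fall well inside. The treatment is also drug plus therapy, so ending the period with the therapy is coherent. This stands as a reason why the numerical effect may be small. It does not explain why the end should vary by up to 20 days between completers.
- **Early leavers are a narrow case.** A reader might infer that the rule removes most events in people who left after a bad session. That needs the last-attended reading, although Protocol Table 1 ends the Treatment Period at the planned Visit 15. Those who fully withdraw consent supply no later AEs (Protocol 4.4.4). Those who stop dosing but remain continue on the planned schedule, and those stopped for a new exclusion criterion stay for the associated Integrative Sessions. What stands for this group is ambiguity, not a demonstrated loss of events.
- **There is no comparison to distort.** The study has one arm. That is true, but the single-arm incidence is itself the result to be reported.

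**Conclusion.** The point holds as a fault of definition. For completers, 0 to 20 days of collected post-dose time (0% to 62.5%) are labelled Follow-up instead of treatment-emergent, about 7 to 12 days with mid-window visits, and the window can close before the 14-day calls end. The 20-day figure needs the earliest Visit 14, the earliest Visit 15 and the latest Visit 16 together. For participants without Visit 15 the SAP does not say when the window closes.

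Against a window that runs to the end of AE collection, the effect on TEAE incidence can only be downward. Its size cannot be estimated: the documents give no AE rate for days 12 to 32 and no distribution of Visit 15 dates. A stronger claim, that TEAE incidence is materially biased or biased most among early leavers, does not follow from what is written. This should be fixed because it is cheap and removes an arbitrary rule, but it does not undermine the safety reporting as a whole.

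**What to change.** In SAP 8.8.2, define a TEAE as any AE with onset, or worsening in severity, after the first IMP dose through Study Termination or last contact, regardless of which Integrative Sessions were attended. Keep the Follow-up Period as a descriptive sub-period of TEAEs, so that early and late events can still be read apart. The worsening clause adds something that the present definition does not address.

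A fixed number of days after the last dose would also remove most of the dependence on scheduling. With 30 days, for illustration only (borrowed from the final-visit provision in Protocol 10.1.7), a completer would lose at most 32 − 30 = 2 days, or 34 − 30 = 4 days with the extra collection days.

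The cost is SAP wording and one programming flag on dates already collected. The downside is that TEAE counts may rise slightly and will include some late events less likely to be drug-related, which the sub-period table would show. The change should be made before database lock, so that it cannot look data-driven. If the Treatment Period is kept as a reporting interval, its stated length should be reconciled: Protocol Table 1 gives 6 to 20 weeks, while Protocol 7.3 and SAP Table 2 give 8 to 20.
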